## **5.2 SECONDARY ENDPOINTS**

### **5.2.1 Secondary endpoints**

The following secondary endpoints will be evaluated in the study:

- Score (0–6) obtained with the Girerd questionnaire at D30, D60 and D90.
- Cumulated dose of oral targeted therapy not taken (all categories) following decision of the medical team.
- Cumulated dose of oral targeted therapy not taken due to dose reduction following decision of the medical team.

- Cumulated dose of oral targeted therapy not taken due to temporary or definitive interruption following the medical team decision.
- Cumulated dose of oral targeted therapy not taken (all categories) following patient decision.
- Cumulated dose of oral targeted therapy not taken due to dose reduction following patient decision.
- Cumulated dose of oral targeted therapy not taken due to temporary or definitive interruption following patient decision.
- VAS score (0–10) for overall patient satisfaction with the level of care (information, advice) at D90.
- Absolute variation observed for the quality of life questionnaire FACT Lung score between D30 and D0, between D90 and D30 and between D90 and D0.
- Number of emergency admissions (related to the treatment) during the 3-month follow-up.
- Number and duration of unplanned hospitalizations (related to the treatment) during the 3-month follow-up.
- Number of unplanned visits to the investigator during the 3-month follow-up.
- Number of unplanned visits to a specialist, whatever is his specialty, other than the investigator during the 3-month follow-up.
- Number of unplanned visits to the general practitioner during the 3-month follow-up.
- VAS score (0–10) for overall investigator satisfaction with the level of patient care at D90.
- VAS score (0–10) for overall general practitioner satisfaction with the level of patient care at D90 (only for the patients with 'remote additional personalised nurse-led follow-up')
- VAS score (0–10) for overall pharmacist satisfaction with the level of patient care at D90 (only for the patients with 'remote additional personalised nurse-led follow-up').
- Number of calls made by the patients to their general practitioner during the 3-month follow-up.
- Number of calls made by the general practitioner to the patient during the 3-month follow-up.
- Number of calls made by the patients to their medical team during the 3-month follow-up.
- Number of calls made by the medical team to their patient during the 3-month follow-up.
- Number of calls between the general practitioners and the medical teams during the 3-month follow-up.

### **5.2.2      Assessment methods**

Girerd questionnaire is a questionnaire composed of 6 binary questions (yes/no) and is used to assess treatment compliance. The final score obtained is the number of questions to which the patient responded 'yes'. Thus, the score ranges from 0 to 6.

FACT Lung quality of life questionnaire is composed of 27 items of the FACT-G questionnaire, with the following 4 dimensions: physical well-being, social well-being,

emotional well-being, and functional well-being. It is composed of 9 questions specific to lung cancer. Each of the 36 questions is scored from 0 to 4 (cf. Section 7.3.3 for more details on the analysis of these questionnaires).

Cumulated dose (mg) of oral targeted therapy not taken between 2 visits is the sum of the doses (mg) of the tablets not taken by the patient. The cumulated dose (mg) of the oral targeted therapy not taken during the 3-month follow-up is the sum of the doses (mg) cumulated not taken between 2 visits during the 3-month follow-up. This dose can be calculated overall and by reason for not taking the prescribed dose: dose reduction, temporary or definitive discontinuation following decision of the medical team / patient decision.

VAS scores will be presented in the form of a horizontal ungraduated line of 10 cm, with the following extremities: left, 'completely unsatisfied' and right, 'very satisfied'. The number of points (0 to 10) obtained in VAS corresponds to the distance (cm) between the left extremity of the line and the mark placed on the line by the patient, investigator, general practitioner, or pharmacist to assess patient's level of satisfaction.

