| Collection of AEs   | X              | X                     | X                     | X                      | X                      | X                      | X                 | X                      | X                      | X                 | X                       | X                             |
| Patient compliance (returned tablets and Girerd questionnaire)                        |                |                       |                       |                        |                        |                        | X                 |                        |                        | X                 |                         | X                             |
| Patient quality of life questionnaire   | X              |                       |                       |                        |                        |                        | X                 |                        |                        |                   |                         | X                             |
| Patient global satisfaction questionnaires  |                |                       |                       |                        |                        |                        |                   |                        |                        |                   |                         | X                             |
| Data collection on use of healthcare services   |                |                       |                       |                        |                        |                        | X                 |                        |                        | X                 |                         | X                             |
| General practitioner and/or pharmacist global satisfaction questionnaires             |                |                       |                       |                        |                        |                        |                   |                        |                        |                   |                         | X                             |
| Investigator global satisfaction questionnaires                                       |                |                       |                       |                        |                        |                        |                   |                        |                        |                   |                         | X                             |

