#### **5.1.2 Assessment methods**

At each visit, patients should bring their oral targeted therapy packet delivered by their pharmacist (empty or started). Missing and remaining tablets will be counted by the medical team and reported in the CRF according to their dose.

The cumulated dose (mg) of the oral targeted therapy, taken between 2 visits, will be calculated as follows: sum of doses (mg) of the tablets used by the patient. Counting the tablets consumed by patients between consultations  $V_{i-1}$  and  $V_i$  will be done by the study team during consultation  $V_i$  from boxes of tablets returned by the patient. The doctor will report, in the CRF, and for each possible dosage (20 mg, 30 mg, 40 mg, 50 mg [only as second intention dose if the treatment is well-tolerated and as per product sheet recommendations]), the number of tablets used by the patient. The cumulated dose between consultations  $V_{i-1}$  and  $V_i$  will be calculated as follows:

$$[\text{Cumulated dose (mg)}]_i = \sum_{\text{Dosages in } \{20, 30, 40\}} [\text{Dosage} \times \text{Ntab(Dosage)}],$$

Where  $Ntab(Dosage)$  is the number of consumed tablets of 20 mg, 30 mg 40 mg or 50 mg respectively.

The cumulated dose (mg) of oral targeted therapy over the 3-month study will be equal to the sum of the cumulated doses (mg) taken between the 2 visits, during the 3-month study. The total cumulated dose (mg) over 3 months will be calculated as follows:

$$\text{Cumulated dose (mg)} = \sum_i [\text{Cumulated dose (mg)}]_i$$

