a Only for patients 'With nurse-led follow-up' group

b Or end of study visit if the patient withdraws prematurely from the study

c Including age, gender, weight, height

d Complete physical exam at inclusion visit including: Vital signs (Heart & respiratory rate, blood pressure, temperature), and collection of the cutaneous, gastro-intestinal, respiratory, eye, cardiovascular and allergic symptoms

e Diagnosis date, disease stage, performance status (ECOG), biopsy date, type of mutation(s), method of mutation typing, previous treatments of NSCLC

f The drug accountability of taken and not taken tablets will be made by the medical team in the Case Report Form

D = day ; M = month ; MV = medical visit according to the routine practice of the centre, NFPC= nurse follow-up phone call, Incl.= inclusion, NSCLC = non-small-cell lung cancer ;

AE= adverse event.

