### **6.2.2 Other visits (MV1, MV2, MV3)**

At the 2nd and 3rd consultation visits (D30 and D60) during which data will be collected, the patient will be asked to:

- Complete the compliance questionnaire (Girerd).
- Complete the quality of life questionnaire (FACT Lung; only on D30).
- Bring their oral targeted therapy packets (empty or started) prescribed/consumed since the previous consultation visit.

- Bring their patient diary.

All the questionnaires will be completed before the start of consultations, in the doctor's office or any other available private place.

The medical team will record the number of tablets taken and not taken, and will report this information in the patient's CRF.

Adverse events and concomitant diseases and medications will be collected during these consultations. Data on the utilization of healthcare services (hospitalizations, emergency room visits, unscheduled consultation visits), including the number of visits and the number of calls to the general practitioner, will also be collected using the information reported by the patient in their patient diary.

During the last consultation visit (MV3 on D90), the patient will be asked to:

- Complete the compliance questionnaire (Girerd),
- Complete the quality of life questionnaire (FACT Lung),
- Complete the global satisfaction questionnaire,
- Bring their oral targeted therapy packets (empty or started) prescribed/consumed since the previous consultation visit,
- Bring their patient diary.

All the questionnaires will be completed before the start of consultations, in the doctor's office or any other available private place.

The medical team will record the number of tablets taken and not taken, and will report this information in the patient's CRF.

Adverse events and concomitant diseases and medications will be collected during these consultations. Data on the utilization of healthcare services will also be collected using the information reported by the patient in their patient diary.

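### Section 5.2.2 defines dose not taken as a tablet count with no reference dose, so six secondary endpoints do not measure the shortfall and can err in either direction

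*Combined protocol and SAP*

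**What the plan says.** **Definition.** Section 5.2.2 says that the dose "not taken between 2 visits is the sum of the doses (mg) of the tablets not taken by the patient", and that the intervals are then summed over three months. It adds: "This dose can be calculated overall and by reason for not taking the prescribed dose". The reasons listed are dose reduction and temporary or definitive discontinuation, each by the medical team or by the patient. The synopsis and Section 2.2.2 repeat the definition. None of these places gives a formula, although the dose taken has an explicit one in Section 5.1.2.

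**Endpoints.** Section 5.2.1 lists six, three for each decision-maker. Two examples are "Cumulated dose of oral targeted therapy not taken (all categories) following decision of the medical team" and "Cumulated dose of oral targeted therapy not taken due to dose reduction following decision of the medical team". Section 7.3.3 plans descriptive statistics by group for them and names no test.

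**Measurement.** Section 5.1.2: "Missing and remaining tablets will be counted by the medical team and reported in the CRF according to their dose". Table 2, footnote f: "The drug accountability of taken and not taken tablets will be made by the medical team in the Case Report Form". The instruction to patients in Section 6.2.2 is "Bring their oral targeted therapy packets (empty or started) prescribed/consumed since the previous consultation visit".

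**Full-dose comparator.** One appears twice, both times for another purpose. Section 7.6 gives 3600 mg for the sample size. Section 7.3.3 uses the uninterrupted, unreduced three-month dose as the denominator of an 80% ratio in an exploratory predictor model. Neither is linked to Section 5.2.2.

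**The concern.** A shortfall needs something to fall short of, and the definition supplies only a count. Two components are then lost: tablets never dispensed after a stop, and the gap between the original dose and a reduced dose that is taken in full. Conversely, higher-strength tablets left over when a dose is reduced count at full strength, although the patient is still being treated.

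The phrase about the prescribed dose does not settle the matter, because a team-ordered change itself alters the prescription. Read as the current prescription, a team reduction that the patient follows scores zero by construction, which would empty the endpoint meant to measure it.

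The primary endpoint, mg taken, pools patient decisions with changes ordered by the team. These six endpoints are the only planned measures in mg that separate the two, and two secondary objectives in Section 2.2.2 rest on them. If the count does not track the shortfall, the described group means and the balance between team-decided and patient-decided shortfall can be wrong even when stop rates are equal in the two arms.

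**Working it through.** **Plan's own figures (Section 7.6).** 40 mg × 90 days = 3600 mg. 3000/3600 = 83.3% and 3180/3600 = 88.3%, as stated. The implied mean shortfalls are 3600 − 3000 = 600 mg without nurse calls and 3600 − 3180 = 420 mg with them. These give the scale for what follows.

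**Assumption.** Pack size and supply are not in the documents. I take packs of p = 7, 14, 28 or 30 tablets, with a new pack supplied only when the last runs out. After d tablets of 40 mg, the leftover is (⌈d/p⌉ × p − d) × 40 mg.

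| Tablets taken | p = 7 | p = 14 | p = 28 | p = 30 |
|---|---|---|---|---|
| d = 20 | 40 mg | 320 mg | 320 mg | 400 mg |
| d = 30 | 200 mg | 480 mg | 1040 mg | 0 mg |

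**Three readings of one patient on 40 mg/day.**

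| Case | Against 3600 mg | Leftover count | Against current prescription |
|---|---|---|---|
| Team stop after D30 | 60 × 40 = 2400 mg | 0 to 1040 mg | 0 mg |
| Patient-decided stop after D30 | 2400 mg | 0 to 1040 mg | 2400 mg |
| Team reduction 40 to 30 mg after D20, all taken | 70 × 10 = 700 mg | 40 to 400 mg | 0 mg |

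The patient in the first row took 1200 mg, so the ratio in Section 7.3.3 is 1200/3600 = 33%, below its 80% cut-off. With 30-tablet packs the leftover count gives the same patient 0 mg not taken.

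**Definitive stops over all stop days, D1 to D89** (leftover capped at the tablets still due by D90). For packs of 7, 14, 28 and 30, the count misses more than half the shortfall on 93%, 85%, 70% and 67% of stop days. There are exceptions. A stop after D75 with 30-tablet packs leaves 15 tablets, or 600 mg, which equals the true 15 × 40 mg. A full 90-day supply in hand also misses nothing.

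**Reductions from 40 to 30 mg over all change days.** For the same packs, the count captures less than half on 71%, 40%, 17% and 16% of days, and exceeds the true shortfall on 12%, 28%, 60% and 64%. Example: a change after D60 with 28-tablet packs leaves 84 − 60 = 24 tablets, or 960 mg, against a true 30 × 10 = 300 mg.

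**Temporary interruptions.** If the same pack is resumed and covers the skipped days, the skipped tablets are still in it. With a 30-tablet pack for D1 to D30 and seven days skipped, 23 are taken and 7 remain: 280 mg = 7 × 40 mg. The count is about right.

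**Check of the fix.** With reference minus taken, split at the prescribed dose, the parts must add up by construction. What the examples test is whether each part lands in the right place.

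- Team stop after D30: 1200 taken + 2400 team + 0 patient = 3600 mg.
- Patient-decided stop after D30: 1200 + 0 + 2400 = 3600 mg.
- Reduction to 30 mg after D20, with three 40 mg and three 30 mg tablets skipped: 2690 + 700 + 210 = 3600 mg.
- Team interruption D31 to D37, then 30 mg to D90: interruption 7 × 40 = 280 mg, reduction 53 × 10 = 530 mg, total 810 mg = 3600 − 2790.
- Last visit at D97, nothing missed: 40 × 97 = 3880 mg gives a shortfall of 0, whereas a fixed 3600 mg would give −280 mg. This is why the reference is scaled to days.

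**The case against.** **The reasons listed imply a pre-change dose.** Naming a team reduction as a reason for not taking the dose makes sense only against the dose intended before the change, and Sections 7.3.3 and 7.6 show what the plan uses as full dose. This is a fair guess at the intent. It does not repair the rule, because Section 5.2.2 states a different one and points to neither section.

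**Remaining tablets and tablets not taken are never equated.** That is true. But the only measurement described is a count from packets, and nothing says how tablets that were never dispensed would enter it.

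**The CRF and the later SAP may fill the gap.** The CRF is not in the documents and may record more. The protocol also mentions stops by decision-maker, the action taken for each adverse event, and the time to the first modification or interruption. These supply neither a reference in mg nor dates for later changes. A SAP can change a definition, but it cannot create dates that were never recorded.

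**Stronger readings that the documents do not support.** A reader might infer that the count misses most of the shortfall after any stop or reduction. It does not: it is about right for the temporary interruptions described, can be exact for a late stop, and can overstate a mid-pack reduction. A reader might also infer that a patient who misses nothing would be scored on tablets left in a started pack at D90, up to (112 − 90) × 40 = 880 mg with 28-tablet packs. Each of the six endpoints requires a team or patient decision, so tablets not yet due belong in none of them; the plan merely lacks a sentence saying so. Finally, no biased comparison between arms has been shown, since the figures are for single patients under assumed supply.

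**Limited consequence.** These endpoints are only described, and discontinuations and reductions are tabulated elsewhere. That lowers the priority but leaves the mg values uninterpretable.

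**Conclusion.** The definition is wrong as written for the six endpoints, and should be corrected; it is more than a missing detail. It names no reference dose, and the count it rests on can understate or overstate the shortfall.

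For a single patient the discrepancy can reach the whole 2400 mg after a D30 stop, or the whole 700 mg after a D20 reduction if the current prescription is used. These compare with implied group mean shortfalls of 600 and 420 mg. The leftover figures depend on the assumed packs and one-at-a-time supply. The absence of a reference, and the zero for a followed team reduction under the current-prescription reading, do not.

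The effect on group means is not quantified. The primary endpoint, the sample size and the Girerd analysis are unaffected.

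**What to change.** In Section 5.2.2, replace the tablet-count definition with: dose not taken in an interval = reference mg − mg taken. The reference is the full-dose comparator already used in Sections 7.3.3 and 7.6, expressed per day and multiplied by the days in the interval, because visits keep their routine timing. Then:

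- Split the result into a team-decided part (reference minus prescribed mg) and a patient-side part (prescribed minus taken mg). A change decided by the patient leaves the prescribed mg unchanged.
- Ensure that the CRF records, for each change, the prescribed dose, start and stop dates, type and decision-maker. Divide each part into reduction and interruption from these records.
- State that leftover tablets not yet due are not counted, and show missed tablets with no recorded decision as a separate unattributed category.
- Have the sponsor state how the reference treats starts below 40 mg, use of the 50 mg strength, intake above the prescription, and early end of follow-up. The documents do not settle these.

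This is a measurement reference only and implies no dosing rule. The cost is wording in Section 5.2.2 and the SAP, a few CRF fields if they are not already there, and a little more site data entry.

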### **5.3 SAFETY DATA TOLERANCE**

#### **5.3.1 Safety endpoints**

The current study will collect the AEs as follows:

- Number of adverse events (AE) related to the oral targeted therapy.
- Number of AE related to the oral targeted therapy of grade  $\geq 3$ .
- Number of serious adverse events (SAE) related to the oral targeted therapy.
- Number of AE related to the oral targeted therapy and leading to a definitive or temporary discontinuation of the drug, or to a dose reduction.

#### **5.3.2 Assessment of adverse events**

The AEs will be collected by the medical team during patient consultation or by the nurse of the specialised call centre Patientys during the follow-up phone call.

The nurse will transmit to the investigator the telephone call report by e-mail or by FAX on the day of the follow-up phone call and will provide [REDACTED] with the AE page(s) of the CRF, if applicable. If needed the nurse may contact the medical team. The investigator will check, confirm, and comment the AEs reported by the nurse. [REDACTED] will add any relevant event. [REDACTED] will also complete the AEs page of the CRF sent by the nurse by adding the intensity and the causal relationship with the oral targeted therapy.

Each AE will be recorded in the CRF and send to the CRO in charge of the data monitoring. The modalities of transmission to the CRO in charge of data monitoring and to the sponsor of the study are described in Sections 3.1, 6.2.3 and 8.4.

### 5.3.2.1      Definition of adverse events

#### **Adverse event**

An AE is defined as any untoward medical occurrence, including an exacerbation of a pre-existing condition, in a person taking part in a clinical study. The event does not necessarily have to have a causal relationship with the study.

#### **Serious adverse event**

A SAE is defined as any AE which:

- Results in death.
- Is immediately life-threatening.
- Results in persistent or significant disability / incapacity.
- Requires or prolongs patient hospitalization.
- Is a congenital anomaly / birth defect.
- Or is considered as medically relevant for any other reasons.

Medical judgment is warranted to determine whether the event or adverse reaction is serious in other situations. Significant reactions or adverse events that are not immediately life-threatening or do not result in death or hospitalization, but may put the subject at risk or may require intervention to prevent the occurrence of one of the above criteria, must also be considered serious.

#### **Intensity of adverse events**

The intensity of adverse events should be classified and recorded according to the CTCAE criteria version 4.03 in the CRF.

